#### **5.3.4. Duration of a Treatment Regimen**

The duration of a given treatment regimen is the time period from the start of the treatment regimen to the end of that treatment regimen. The duration will stop and start for each treatment regimen change. If a patient is treated in a given treatment regimen more than once, the total durations in the same treatment regimen will be added together. For example, if a patient is treated with the prophylactic regimen and then undergoes surgery and then goes back to the prophylactic regimen, then his total duration in the prophylactic regimen will be the sum of the two durations in the prophylactic regimen. Further details will be provided for individual analysis where needed.

The total duration of time allocated to each treatment regimen will be calculated in minutes and converted to days as the number of minutes divided by 1440.

### **5.4. Study Periods**

#### **5.4.1. Screening Period**

The screening period starts after a patient signs the study consent form and ends immediately prior to administration of the first dose of study drug rFIXFc.

#### **5.4.2. Efficacy Period**

The efficacy period will be used for the evaluation of efficacy and health outcome endpoints. For a patient to have an evaluable efficacy period over the duration of study, he must have at least 1 day of treatment for an episodic regimen or at least 2 prophylactic injections for prophylactic regimens.

The start and end, and the total duration of the efficacy period for a given treatment regimen is the same as the start and end, and the total duration of that treatment regimen defined in Section 5.3.4 with the exceptions described in the following two subsections. The start of the efficacy period for each patient is the start of their first treatment regimen and the end is the end of their last.

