Statistical Methods:	In general, all statistical analyses will be descriptive in nature. No formal comparison is planned and no hypothesis will be formally tested. Continuous variables will be summarized and presented by the number of observations, mean, median, standard deviation, minimum, and maximum. Categorical variables will be summarized by the number and percentage in each category. Subjects with at least 1 dose of rFIXFc (study drug and/or commercially available rFIXFc) will be included in the Safety Analysis Set. Subjects with at least 1 dose of rFIXFc

CONFIDENTIAL

study drug will be included in the Full Analysis Set (FAS). Subjects with at least 1 dose of rFIXFc study drug and who meet the eligibility criteria (with screening FIX activity and inhibitor test results confirmed by the central laboratory) will be included in the Supporting Analysis Set. Efficacy analyses will be based on the FAS. Safety analyses will be based on the Safety Analysis Set, with some analyses based on the Supporting Analysis Set, as appropriate. Subjects developing a confirmed positive inhibitor test after exposure to rFIXFc study drug will have their efficacy and safety data included up to the time of the last negative inhibitor test; efficacy and safety data collected after the time of the last negative inhibitor test will be summarized separately. Summary statistics will be presented for safety and efficacy endpoints. The proportion of subjects developing inhibitors will be presented with a 95% confidence interval. For efficacy purposes, the number of bleeding episodes will be annualized. The summary statistics of bleeding episodes per person-year and subject's response to treatment will be presented separately for episodic and prophylaxis treatment. Other statistical analyses may be conducted for exploratory purposes.

Interim Analysis:

No interim analyses are planned for this study.

Sample Size Determination:

Because the size of the hemophilia population is limited, the sample size is based on clinical rather than statistical considerations. Taking into account the CHMP Guideline [[EMA \(EMA/CHMP/BPWP/144552/2009\) 2011](#)] and in an effort to enroll a sufficient number of subjects to assess the efficacy and safety of rFIXFc in this population of primarily very young children, approximately 30 subjects will be enrolled to achieve at least 20 subjects with no less than 50 EDs by the completion of the study.

Study Stopping Rules:

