16.2. Efficacy

16.2.1. Analysis Population

Subjects who receive at least 1 dose of rFIXFc study drug will be included in the FAS. Efficacy analyses will be based on the FAS including the data collected on or after the time of the first injection of rFIXFc study drug.

Subjects developing a confirmed positive inhibitor test after exposure to rFIXFc study drug (the Inhibitor Subgroup) will have their efficacy data included up to the time of the last negative inhibitor test; efficacy data collected after the time of the last negative inhibitor test will be summarized separately.

CONFIDENTIAL

The information contained herein may not be used, disclosed, or published without the written consent of Bioverativ Therapeutics Inc

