16.2.2. General Methods of Analysis

All efficacy endpoints are secondary. No imputation will be applied to any missing efficacy data.

The efficacy and surgical/rehabilitation periods will be defined in the statistical analysis plan (SAP) for the purpose of determining the study periods during which data will be used for select efficacy analyses. Data on bleeding and rFIXFc consumption will be based on the efficacy period; surgical evaluations will be based on the surgical/rehabilitation period.

Analysis of efficacy endpoints that are visit-based will include data from all study visits whether or not in the efficacy period, unless that visit is coincidental with a surgical/rehabilitation period for a major surgery, in which case it would be excluded.

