16.5. Safety

Unless specified otherwise in the SAP, safety data will be summarized overall. Subjects developing a confirmed positive inhibitor test after exposure to rFIXFc study drug (the Inhibitor Subgroup) will have their safety data included up to the time of the last negative inhibitor test; safety data collected after the time of the last negative inhibitor test will be summarized separately.

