#### **5.4.5. Safety Period**

The overall safety period is defined as beginning at the first dose of study medication rFIXFc. For patients who are subsequently enrolled, the safety period ends on the date of the Final Safety Follow-up Visit (by telephone or in person), 14 (+7) days after the last dose of rFIXFc. For patients who fail screening, this period ends on the date that this is confirmed.

The safety period on a specific treatment regimen is as described in Section 5.3 except that the end of the patient's last treatment regimen is the end of their safety period.

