### 9.3. Adverse Events

An adverse event (AE) is any untoward medical occurrence in a patient or clinical investigation subject administered a pharmaceutical product that does not necessarily have a causal relationship with this treatment. An AE can therefore be any unfavorable and unintended sign (including an abnormal laboratory finding), symptom, or disease temporally associated with the use of a medicinal (investigational) product, whether or not related to the medicinal (investigational) product.

Bleeding episodes in this patient population are not considered as AEs. Bleeding episodes that meet a serious criterion should be reported as serious adverse events (SAE).

AEs will be classified using the Medical Dictionary for Regulatory Activities (MedDRA) system organ classes and preferred terms. MedDRA version 21.1 will be used in this study. All AEs will be listed.

The incidence of AEs will be summarized by system organ class (SOC) and preferred term (PT). Summaries will be included for all AEs as well as by severity and relationship to treatment. Patient listings will be provided for all AEs, SAEs, related AEs, AEs resulting in discontinuation of study treatment and/or withdrawal from the study, AEs during major surgical/rehabilitation periods, and deaths.

AEs that occurred during major surgical/rehabilitation periods will be included in the overall (top-line) summary of AEs but not in any of the other AE tables. Consideration is given to adverse events with an onset date at the start of the surgical/rehabilitation period in the event the pre-surgical dose was administered the day before the surgery.

All AE listings will include the onset and resolution study days relative to Study Day 1, which is the date of the first rFIXFc treatment. AEs that are emergent prior to the first rFIXFc treatment, AEs that are emergent during a major surgical/rehabilitation period, and AEs that are emergent on the day of surgery will be flagged. Similarly, AEs that are emergent after inhibitor development will be indicated separately as per the period during which they occurred.

Events of overdose will not be included in the AE summary tables unless they are determined to be AEs.

	Statistical Analysis Plan	Final v1.0
---	----------------------------------	-------------------

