## 10. CHANGES TO PLANNED ANALYSIS

This SAP is based on Version 3 of the approved study protocol dated 06 August 2018. The major differences in the analysis described in this SAP compared to the protocol are:

- The Full Analysis Set consists of all patients who received at least 1 dose of rFIXFc and were enrolled.
- The protocol mentioned selected analyses may be performed based on a Supporting Analysis Set as appropriate. This analysis set is not defined in the SAP, and all analyses will be based on the analysis populations defined in Section 4.
- The health outcomes questionnaire used in the study is not as specified in the protocol. The analysis described refers to that which was actually used and this can be found in [Appendix A](#).

	Statistical Analysis Plan	Final v1.0
---	----------------------------------	-------------------

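### The SAP drops, without declaring it, the protocol's cut-off at the last negative inhibitor test, so post-inhibitor data outside ITI stay in the episodic and prophylaxis summaries

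*SAP*

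**What the plan says.** The protocol states the rule three times. The Synopsis (Statistical Methods) says that "efficacy and safety data collected after the time of the last negative inhibitor test will be summarized separately". Section 16.2.1 repeats it for efficacy: "efficacy data collected after the time of the last negative inhibitor test will be summarized separately". Section 16.5 repeats it for safety: "safety data collected after the time of the last negative inhibitor test will be summarized separately". In each place the subject's data count in the main summaries up to that test. Protocol 16.2.2 leaves the definition of the efficacy period to the SAP, so SAP 5.4.2 is where the rule should appear.

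SAP 5.4.2 fixes both limits by the treatment regimens alone: "the efficacy period for each patient is the start of their first treatment regimen and the end is the end of their last". It allows two exceptions: surgical/rehabilitation periods (5.4.2.1) and gaps of more than 28 days between injections on prophylaxis (5.4.2.2). SAP 5.4.5 takes the by-regimen safety period from the regimen dates, except that the end of the patient's "last treatment regimen is the end of their safety period". SAP 5.1.1 places all time spent on a regimen in that regimen's column.

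SAP Section 10 opens with "The major differences in the analysis described in this SAP compared to the protocol are" and gives three items: the Full Analysis Set, the dropped Supporting Analysis Set and the health outcomes questionnaire. The cut-off is not among them.

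**The concern.** The episodic and prophylaxis tables produced under the SAP would not be the ones the protocol describes, and the SAP does not tell the reader so.

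Post-inhibitor data can differ in kind from earlier data. Under Protocol 10.2.6.2 low-titer subjects may stay on study with a higher dose per injection. Under Protocol 10.2.6.4 bypassing agents are allowed once an inhibitor is confirmed or suspected, and SAP 7.4.8 counts bleeds treated with non-study medication in the injections-per-bleed endpoint. Bleeding rate, consumption, bleed-treatment and adverse event summaries would therefore mix two states that the protocol keeps apart.

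**Working it through.** **Does another SAP provision supply the cut-off?** The SAP nowhere refers to the last negative inhibitor test. Three provisions come close.

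- The ITI column (5.1.1) separates ITI time only.
- The display by inhibitor status (5.1.1) covers selected tables, needs at least 5 positive patients, and divides patients rather than time before and after the inhibitor.
- SAP 9.3 says that "AEs that are emergent after inhibitor development will be indicated separately as per the period during which they occurred". This stands in the paragraph on listings. It sets no cut-off for the adverse event tables and does not cover bleeding or consumption.

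The list of tables in SAP Section 12 has no post-inhibitor summary outside ITI.

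**Which time is affected?**

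- Low-titer subjects who stay on regimen. Protocol 10.2.6.2 keeps them on study, and SAP 9.4.3.4 expects such patients. All their regimen time after the cut-off stays in the columns.
- High-titer subjects, and low-titer subjects whose bleeding is no longer controlled, who enter ITI or withdraw. The interval from the last negative test to that point stays in. Interim visits are nominally 12 weeks apart (Protocol 7.3.2) and confirmation takes 2 to 4 weeks (Protocol 10.2.4). The last negative test can therefore precede confirmation by about 12 + 2 = 14 to 12 + 4 = 16 weeks, or less if an exposure-day milestone or unscheduled test falls between.

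**How large is the effect?** The documents give no figure to reproduce. The illustration below takes 30 subjects from Protocol 16.7. Everything else is assumed: one year each, ABR 3 in every subject before any inhibitor, and one inhibitor case. Let *f* be the fraction of his regimen time after the last negative test and *p* his ABR in that time. By the ABR formula in SAP 7.4.3:

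- with the cut-off, his ABR is 3 and the group mean is 3.00;
- without it, his ABR is 3(1 − *f*) + *pf*, and the group mean is (29 × 3 + his ABR)/30.

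| *f* | *p* | His ABR | Group mean | Change |
|---|---|---|---|---|
| 0.2 | 3 | 3.0 | 3.00 | 0% |
| 0.2 | 6 | 2.4 + 1.2 = 3.6 | 90.6/30 = 3.02 | +0.7% |
| 0.2 | 10 | 2.4 + 2.0 = 4.4 | 91.4/30 = 3.05 | +1.6% |
| 0.6 | 3 | 3.0 | 3.00 | 0% |
| 0.6 | 6 | 1.2 + 3.6 = 4.8 | 91.8/30 = 3.06 | +2.0% |
| 0.6 | 10 | 1.2 + 6.0 = 7.2 | 94.2/30 = 3.14 | +4.7% |

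The *f* = 0.2 rows represent a subject who goes to ITI or withdraws; the *f* = 0.6 rows represent a low-titer subject who stays on regimen. In the last row 6.0 of 87 + 1.2 + 6.0 = 94.2 bleeds (6.4%) in the per-bleed tables are post-inhibitor. The median stays at 3.00 and the maximum rises to 7.2, but both follow from giving every other subject the same rate.

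For consumption with *f* = 0.6 and a post- to pre-cut-off rate ratio *r*, the relative mean is (29 + 0.4 + 0.6*r*)/30. This is 1.000, 1.010 and 1.020 for *r* = 1, 1.5 and 2.

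A wider range uses rates cited in Protocol 5.1.1: 3.5 per year beforehand (midpoint of the 3 to 4 spontaneous bleeds on prophylaxis, as a stand-in for all bleeds) and, as an upper bound afterwards, 20 per year (the episodic figure). If half the year falls after the cut-off, his ABR is 1.75 + 10 = 11.75. One such subject in 30 gives (29 × 3.5 + 11.75)/30 = 3.78. Two in 20 give (18 × 3.5 + 2 × 11.75)/20 = 4.33. The mean shift is then 0.28 to 0.83 bleeds per year, and zero if the rate does not change.

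**The case against.** The protocol wording is less exact than it looks. It does not say that the last negative test must precede the first positive. A low-titer subject who returns to negative without ITI (SAP 9.4.3.4) has a later negative test, and on a literal reading little of his time would be cut. This stands as a reason to fix the wording. It does not excuse having no cut-off.

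The largest illustration is also a corner case. A low-titer subject whose bleeding more than triples would probably be judged uncontrolled and become eligible for ITI, with withdrawal if he declines (Protocol 10.2.6.2). The rows from +0.7% to +2.0% are the more likely ones, and the movement in the maximum might vanish with real spread between subjects.

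The safety half is weaker. Protocol 16.5 opens by letting the SAP specify otherwise, and post-inhibitor adverse events can be found in the listings. That opening clause belongs to the sentence on summarising safety data overall, while the cut-off is a separate sentence, but the departure is clearest for efficacy.

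Finally, the analyses are descriptive, the study has about 30 subjects, and the listings would let a reader trace each inhibitor case. All true, but a reader of the summary tables would still not know that the protocol rule had been set aside.

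**Conclusion.** The concern holds. The SAP's period rule conflicts with an explicit protocol rule, and Section 10 does not declare it. Followed as written, it puts post-inhibitor, non-ITI data into the episodic and prophylaxis summaries. That conclusion rests on the texts alone.

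The numerical effect depends on the assumed rates and time split. It is nil if no subject develops an inhibitor or if rates do not change, up to +4.7% on the mean ABR for one case in 30 under the first set of assumptions, and up to about 0.8 bleeds per year under the wider set with two cases in 20. The primary endpoint is untouched. This should be fixed, but it does not threaten the study's main conclusion.

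**What to change.** In SAP 5.4.2 and 5.4.5, state that for Inhibitor Subgroup subjects the episodic and prophylaxis periods used in the main summaries end at the last negative inhibitor test before the first confirmed positive sample. Put later non-ITI data in a separate post-inhibitor summary, or in a listing if there are few subjects. Leave the ITI column as it is. State how time after remission without ITI is handled.

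State also whether the cut-off applies to incremental recovery. SAP 7.1 takes visit-based efficacy endpoints from all visits whether or not they fall in the efficacy period, so a change to 5.4.2 alone may not reach it.

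If the sponsor means to depart from the protocol rule, declare and justify that in Section 10 and show the results with the cut-off as a sensitivity analysis. The 5-patient condition in SAP 5.1.1 governs a different display and can stay.

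The cost is one period rule in two sections and one extra summary or listing. The main tables lose a little person-time.

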##### **5.4.2.1. Adjustments Due to Surgical/Rehabilitation Periods**

For analysis purposes, the efficacy period for a given treatment regimen will be adjusted for all surgical/rehabilitation periods (major and minor). The start and end of the efficacy period for a given treatment regimen are adjusted as follows:

	Statistical Analysis Plan	Final v1.0
---	----------------------------------	-------------------

- For patients on a prophylactic regimen before the start of a surgical/rehabilitation period, the efficacy period for the prophylactic regimen continues up to the last dose (for prophylaxis or bleeding) before the start of the surgical/rehabilitation period.
- For patients on the episodic regimen before the start of a surgical/rehabilitation period, the efficacy period for the episodic regimen continues up to 1 minute before the start of a surgical/rehabilitation period.
- For patients on a prophylactic regimen following the end of a surgical/rehabilitation period, the efficacy period for the prophylactic regimen starts or re-starts at the first prophylactic dose following the end of the surgical/rehabilitation period.
- For patients on the episodic regimen following the end of a surgical/rehabilitation period, the efficacy period for the episodic regimen starts or re-starts at 00:01 on the day following the end of the surgical/ rehabilitation period.

Start and end dates/times for the efficacy period for given treatment regimens and treatment regimen changes will be adjusted for each surgery (major or minor) as necessary.

For patients on a prophylactic regimen before the start of a surgical/rehabilitation period, the interval of time between the last dose before the surgical/rehabilitation period and the start of the surgical/rehabilitation period will not be attributed to the efficacy period for the prophylactic regimen. By definition, there should not be any treated bleeding episodes in this interval of time.

For patients on a prophylactic regimen following the end of a surgical/rehabilitation period, bleeding episodes that occur after discharge from a rehabilitation facility but before the next prophylactic dose will be attributed to the surgical/rehabilitation period and hence not counted towards the annualized bleeding rate (ABR).

#### **5.4.2.2. Adjustments Due to Large Injection Intervals**

For analysis purposes, the efficacy period will also be adjusted to account for large intervals between injections resulting from missing data. A large interval is defined as >28 days between any 2 adjacent rFIXFc injections within a prophylactic treatment regimen and any such intervals will be removed from the efficacy period. The efficacy period prior to each such interval will end at the time of the first injection of this interval and restart (or start if it is the first interval of a treatment regimen) at the time of the second injection of this interval. The efficacy period will be adjusted for each identified interval that is not within a surgical/rehabilitation period. This algorithm applies only to prophylactic regimens and no adjustment for large injection intervals will be made for episodic treatment regimens.

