10.7. Treatment Compliance

Compliance with treatment dosing is to be monitored and recorded by site staff. The instructions provided in the DHA must be followed, as summarized in Section 10.1.1 of this protocol.

For the doses that will be administered at the study site, the study treatment will be administered under controlled conditions by the investigational staff; therefore, full compliance with study treatment is anticipated.

For between visit administration, subjects' parents or caregivers will administer (or older children will self-administer) rFIXFc and will record treatment in the EPD. The EPD will be reviewed during periodic calls to the subject's parents/caregiver and at each clinic visit.

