### 6.6.1.3. Prophylactic Dose (IU/kg) and Dosing Interval (days)

The prescribed prophylactic dose and dosing frequency will be summarized descriptively for the prophylactic and ITI treatment periods.

Because dosing in this study is based on variable doses and dosing intervals, average weekly dose [REDACTED] and average dosing interval will be derived for each patient to characterize the amount of rFIXFc received for prophylaxis. Descriptive statistics will be provided using the FAS.

The average weekly [REDACTED] prophylactic dose (IU/kg) and the average prophylactic dosing interval will be based on prophylactic doses that are not separated by a bleeding episode or major surgical/rehabilitation period. Data to be included in the calculations, specifically the prophylactic doses and the total duration of prophylactic treatment, will come strictly from intervals representing two consecutive prophylactic doses (PR) during the efficacy period (see Section 5.4.2 for a description of the efficacy period). The sum of doses at PRx and the sum of interval durations (PRx+1 – PRx), will be determined across all evaluable intervals of PRx to PRx+1. As such, when an event (a bleeding episode or surgery) is encountered, the interval stops at the prophylactic dose prior to the event and continues with the first prophylactic dose after the event. The last PR dose in the study will be the end of the last interval used for these calculations.

$$\text{Average weekly prophylactic dose} = \frac{\text{Sum of doses at PR}_x \times 7}{\text{Sum of days in PR intervals}}$$

$$\text{Average daily prophylactic dose} = \frac{\text{Sum of doses at PR}_x}{\text{Sum of days in PR intervals}}$$

$$\text{Average prophylactic dosing interval} = \frac{\text{Sum of days in PR intervals}}{\text{Number of PR intervals}}$$

Prophylactic dosing will be further characterized by the number of prescribed changes in the dose and the number of prescribed changes in the dosing interval. Dose and dosing interval changes are based on recommendations made by the Investigator and may or may not reflect whatever modifications a patient actually made to his dosing regimen. The number of prescribed changes in the dose level and the number of prescribed changes in the dosing schedule will be summarized categorically (0, 1, 2, 3, 4, >4) and with descriptive statistics.

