**6.6.2.2. Compliance of Prophylactic Injections**

The compliance rate of each patient to the prescribed prophylactic and ITI dosing regimens during the efficacy period will be calculated in 2 ways: As dose compliance and as dosing interval compliance. Compliance will first be determined on a per-injection basis and then on a per-patient basis. That is, compliance for an individual dose or dosing interval will be determined and then the overall percentage of doses and dosing intervals that were in compliance will be determined for each patient.

For the purpose of evaluating compliance, the following will be considered per injection:

- The nominal dose taken compared to the nominal dose prescribed
- The actual day of treatment compared to the prescribed day of treatment

An individual dose will be considered compliant if it is within 80%-125% of the prescribed dose. An individual dosing interval will be considered compliant if the time between two prophylactic doses is within 36 hours of the prescribed dosing interval. Prescribed dose and dosing intervals are according to the Investigator. Instructions provided to the patient by the Investigator regarding dose or dosing interval changes will be used to determine compliance as of the date the information was provided to the patient.

The actual dosing intervals will be calculated as the length of time between consecutive prophylactic doses (date/time of PRx+1 – date/time of PRx), PRx+1 and PRx. The actual time between doses will be determined in minutes and converted to days as the number of minutes divided by 1440. The prescribed dosing interval will be taken from the eCRF as recorded by the Investigator. The absolute value of the difference between the actual and prescribed dosing intervals must be ≤ 1.5 day (+/- 36 hours) in order to be compliant [REDACTED]

All prophylactic injections will be used to determine prophylactic dose compliance; only the prophylactic injections used to determine the average prophylactic dosing interval (i.e., intervals not separated by a bleeding episode or surgical/rehabilitation period), as detailed in Section 5.4, will be used to evaluate prophylactic interval compliance. Dose and dosing interval compliance rates per patient will be determined as follows:

$$\text{Dose compliance rate} = \frac{\text{Number of doses taken within 80\%-125\% of prescribed dose}}{\text{Total number of doses}} \times 100$$

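### The 28-day gap rule in SAP 5.4.2.2 removes lapses in prophylaxis without checking their cause, and a treated bleed inside a lapse can decide whether its time is removed

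*SAP*

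**What the plan says.** SAP 5.4.2.2 gives its purpose as a correction for "large intervals between injections resulting from missing data". The rule itself has no missing-data condition. It reads "A large interval is defined as >28 days between any 2 adjacent rFIXFc injections within a prophylactic treatment regimen". Removal then follows automatically, with no step to check the cause. The efficacy period stops at the first injection of the gap and restarts at the second.

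There are two carve-outs. Gaps on the episodic regimen are not adjusted. Nor are gaps in a surgical period: "The efficacy period will be adjusted for each identified interval that is not within a surgical/rehabilitation period". Surgical time is already excluded by SAP 5.4.2.1.

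Three other provisions matter:

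- After eligibility, bleeds are to be treated with rFIXFc study drug (Protocol 10.2.3.4), so a treated bleed creates an rFIXFc injection.
- A bleeding episode starts at the first sign of the bleed (SAP 5.2.4), which precedes its injection.
- Days in the efficacy period are the denominator of the ABR (SAP 7.4.3) and of annualized consumption (SAP 6.6.1.4).

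**The concern.** A long gap in the injection record can mean two things: doses given but not entered, or doses not given. The site looks at the diary during the study ("The EPD will be reviewed during periodic calls to the subject's parents/caregiver and at each clinic visit"), so a gap that survives to analysis may well be a real lapse. The rule treats both alike.

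The larger difficulty is that any rFIXFc injection ends a gap. Suppose two boys both miss prophylaxis for 42 days. One has a treated bleed on day 20. His gaps are 20 and 22 days, so all 42 days stay in and the bleed counts. The other does not bleed, and his 42 bleed-free days are deleted. Lapse time is kept or dropped according to the event being counted.

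A boundary case is also open. If a bleed injection closes a gap of more than 28 days, the onset lies in deleted time and the injection in kept time. SAP 5.4.2.1 settles the matching question after surgery; 5.4.2.2 does not. Two programmers could report different ABRs from the same data.

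**Working it through.** The documents give no figure to reproduce, and neither the frequency nor the length of lapses. What follows is illustration under stated assumptions.

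**Inputs.** Lapse L = 42 days (assumed). Bleeds are Poisson at 2 a year, in and out of the lapse (assumed), so the true ABR is 2.0. Follow-up T = 350 days (50 EDs at the recommended weekly start, 50 × 7) or 182 days (the 26-week subgroup of SAP 7.4.3). ABR = bleeds / days kept × 365.25 (SAP 7.4.3).

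**Which days survive.** One bleed on lapse day x leaves pieces of x and 42 − x days. Both are 28 days or less only if x lies between 14 and 28, so one position in three keeps the whole lapse. In general one bleed can save a whole lapse only up to 28 + 28 = 56 days.

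**T = 350.** Expected bleeds in the lapse: 2 × 42/365.25 = 0.230, so P(none) = exp(−0.230) = 0.795, P(one) = 0.183, P(two or more) = 0.023. Expected bleeds outside it: 2 × 308/365.25 = 1.687.

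- No lapse bleed: 1.687/308 × 365.25 = 2.00. With all time kept it would be 1.687/350 × 365.25 = 1.76.
- One bleed, days 14 to 28: 2.687/350 × 365.25 = 2.80.
- One bleed, before day 14: the removed piece averages 35 days, so 2.687/315 × 365.25 = 3.12.
- One bleed, after day 28: 3.12 if the closing bleed counts, or 1.687/315 × 365.25 = 1.96 if it is dropped.
- Mean with one bleed: (2.80 + 3.12 + 3.12)/3 = 3.01 counted; (2.80 + 3.12 + 1.96)/3 = 2.63 dropped.
- Two or more bleeds (simulated): 4.05 counted, 3.81 dropped.

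Counted: 0.795 × 2.00 + 0.183 × 3.01 + 0.023 × 4.05 = **2.23**. Dropped: 0.795 × 2.00 + 0.183 × 2.63 + 0.023 × 3.81 = **2.16**.

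**T = 182.** Bleeds outside the lapse: 2 × 140/365.25 = 0.767. No lapse bleed: 2.00. One bleed: 1.767/182 × 365.25 = 3.55 if it falls on days 14 to 28, otherwise 1.767/147 × 365.25 = 4.39, or 0.767/147 × 365.25 = 1.91 if a closing bleed is dropped. The means are 4.11 and 3.28. Two or more (simulated): 6.10 and 5.57. Totals: 0.795 × 2.00 + 0.183 × 4.11 + 0.023 × 6.10 = **2.48**, and 0.795 × 2.00 + 0.183 × 3.28 + 0.023 × 5.57 = **2.32**.

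**Other assumptions.** Simulated mean ABR of a lapsing patient over 364 days. The 3.5 and 20 a year are anchored on Protocol 5.1.1; the rest are assumed.

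| Lapse (days) | Bleeds/yr dosed, lapsed | All time kept | Rule, by injection | Rule, by onset |
|---|---|---|---|---|
| 42 | 3.5, 3.5 | 3.50 | 3.86 | 3.74 |
| 84 | 3.5, 3.5 | 3.50 | 4.39 | 3.88 |
| 42 | 3.5, 20 | 5.40 | 5.57 | 5.39 |
| 84 | 1, 10 | 3.07 | 3.58 | 2.72 |

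Across all scenarios run, the change against keeping all time was about +2% to +28% dated by injection and −11% to +11% dated by onset.

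**Cohort mean.** With 10% to 33% of patients lapsing, three scenarios were run (42 days at 1 and 10 a year; 42 and 84 days at 3.5 and 20 a year). The shift was +0.02 to +0.24 bleeds a year by injection (about +0.5% to +5%) and −0.03 to 0 by onset. An 84-day lapse that leaves bleeding unchanged, in 33% of patients, would give more: 0.33 × (4.39 − 3.50)/3.50 = +8%.

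**Consumption.** For a bleed-free 42-day lapse, annualized consumption rises by T/(T − L): 350/308 = 1.14, or 182/140 = 1.30. A bleed between days 14 and 28 leaves the denominator whole.

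**The case against.** The rule is fixed in advance and involves no judgement. The diary is the primary source for bleeds (Protocol 10.2.3.1), so a true diary gap can lose bleeds as well as injections, and removing it is reasonable. That stands. It also tells against deciding each gap by case review: undetermined gaps left in would add falsely bleed-free time, and the reviewers in an open-label study would see the bleeds.

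A stop recorded as a change to episodic treatment is not lost. SAP 5.3.3 ends prophylaxis at the last prophylactic dose and starts episodic time one minute later, where no gap is removed. This stands and limits the point to lapses never recorded as a change.

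Some transparency exists. SAP 7.4.2 summarizes unadjusted bleed counts, and all injections and treated bleeds are listed. But the patient-years beside those counts are again those of the efficacy period, and neither SAP 7.4.3 nor the table list in section 12 contains an ABR without the adjustment.

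A reader might infer that the rule flatters dosing-interval compliance and that correcting it would repair this. The documents do not support that. The dosing-interval data "will come strictly from intervals representing two consecutive prophylactic doses (PR) during the efficacy period", and SAP 6.6.1.3 and 6.6.2.2 already leave out intervals separated by a bleed. A lapse containing a treated bleed leaves interval compliance whatever 5.4.2.2 says.

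**Conclusion.** The defect is real and worth correcting before lock. The rule does not match its stated purpose, exclusion depends on the outcome, and the boundary bleed is undefined. For a patient with an unrecorded 42-day lapse and unchanged bleeding, the ABR is overstated by about 8% to 12% over 350 days and 16% to 24% over 182 days. The cohort effect is probably small, roughly 0 to +5% in the scenarios run, though not capped there. All of this rests on assumed lapse lengths, bleed rates and lapse frequency.

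Two stronger readings fail. One is that the main efficacy result is compromised: ABR is one of seven unranked secondary endpoints (Protocol 6.2.2), all analyses are descriptive (Protocol 16), and the primary inhibitor endpoint does not use the efficacy period. The other is that the bias has a known direction. Deleting bleed-free time raises the ABR, which works against the product; dropping closing bleeds lowers it. The net sign depends on a dating rule that the SAP does not give.

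**What to change.** 1. In SAP 5.4.2.2, define the interval of more than 28 days between consecutive prophylactic doses, ignoring injections for bleeds. When an interval is removed, remove its time and every bleed with onset in it.
2. State that boundary bleeds are assigned by onset.
3. Report one sensitivity ABR and one sensitivity annualized consumption with no large-interval removal, keeping all prophylaxis time and bleeds.

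The cost is SAP wording and two added tables, with no new data. The downside is that bleeds during long lapses leave the main ABR, which favours the product if lapses raise bleeding; the sensitivity analysis shows how much. With 2 bleeds a year while dosed, 6 in a 42-day lapse, and 350 days, the main ABR would be about 1.99 and the sensitivity ABR about 2.47. The current rule gives 2.68 or 2.51, matching neither. The change does not alter interval compliance, which has its own exclusions.
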